#### **4.1.2 General Considerations for Summary of Safety Data**

The following considerations are for the summary of safety data.

- The missing values in ECG, vital signs, laboratory data, coagulation and urinalysis will not be imputed.
- If triple ECGs are performed, the mean value of any continuous parameters of the ECG will be derived first and it will be used as the value of the ECG at that timepoint/assessment. For abnormalities, the worst case will be used for any summary tables.
- If a laboratory value is reported as <LLQ (where ‘LLQ’ is the lower limit of quantification), then LLQ value will be used to impute ‘<LLQ’ for the summary tables. In the data listings, this value will be listed as reported <LLQ.
- Any TEAEs with missing causality data will be considered as related to the durvalumab.
- Any partial dates will be presented as reported in the data listings. The partial dates will be imputed for the derivation of time to resolution, time to onset etc. using the criteria given in Section 4.1.3.

#### **4.1.3 Handling of Missing Data**

Missing safety data will generally not be imputed. However, safety assessment values of the form of “<x” (ie, below the lower limit of quantification) or >x (ie, above the upper limit of quantification) will be imputed as “x” in the calculation of summary statistics but displayed as “<x” or “>x” in the listings.

If the start date of the concomitant medication or AE is missing, the following rules will be applied:

- If the year is missing, the year should be imputed as the year that patient received the first dose of durvalumab.
- If the year is available and the month and day are missing, then impute the month as January and the day as 01 unless year is the same as first dose date then impute first dose date.
- If the year and month are available and the day is missing, impute the day as 01 (the first day of the month) unless month is same as month of first dose of study drug then impute first dose date.

- If the start date is completely missing and end date is present, then take day and month as 01Jan and the year from end date.

If the stop date of the concomitant medication or AE is missing, the following rules will be applied:

- If the year is missing, the year should be imputed as the year that patient received the last dose of durvalumab.
- If the year is available and the month and day are missing, then impute the month as December and the day as 31 unless year is the same as last dose date then impute last dose date. If the last dose date is not available then DCO date will be used.
- If the year and month are available and the day is missing, impute the day as the last day of the month (eg, 28, 29, 30 or 31) unless month is same as month of last dose date then impute last dose date. If the last dose date is not available, DCO date will be used.
- If the end date is completely missing, then look at whether the AE/medication is still ongoing before imputing a date and also when it started in relation to study drug. If the ongoing flag is missing then assume that AE is still present / medication is still being taken (i.e. do not impute a date). If the AE/medication has stopped and start date is prior to first dose date then impute the 1st dose date, if it started on or after first dose date then impute a date that is 1 day after the last dose date.
- It is not expected to have missing dates for unscheduled laboratory, ECG, diagnostics data. However, if there are missing dates, for any derivations, the dates should be imputed following the rules for stop date of concomitant medications and AEs

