8.3.2 Time period and frequency for collecting AE and SAE information

AEs and SAEs will be collected from the time of the patient signing the ICF until 90 days after the last dose of durvalumab. If an event that starts after the defined safety follow-up period noted above is considered to be due to a late onset toxicity to study drug, then it should be reported as an AE or SAE as applicable.

All SAEs will be recorded and reported to the Sponsor or designee within 24 hours, as indicated in [Appendix B](#). The Investigator will submit any updated SAE data to the Sponsor within 24 hours of it being available.

Investigators are not obligated to actively seek AEs or SAEs in former study patients. However, if the Investigator learns of any SAE, including a death, at any time after a patient's last visit and he/she considers the event to be reasonably related to the study treatment or study participation, the Investigator should notify the Sponsor.

The method of recording, evaluating, and assessing causality of AEs and SAEs and the procedures for completing and transmitting SAE reports are provided in [Appendix B](#).

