### **3.2.3 Adverse Events**

AEs and SAEs will be collected throughout the study, from time of the patient signing the informed consent and 90 days after the last dose of durvalumab. A treatment emergent adverse event (TEAE) is an AE with an onset date or a pre-existing AE worsening following the first dose of study treatment through to 90 days after the last dose of durvalumab.

The Medical Dictionary for Regulatory Activities (MedDRA) (using the latest or current MedDRA version) will be used to code the AEs. AEs will be graded according to the National Cancer Institute Common Terminology Criteria for AEs (CTCAE Version 5.0). The meaning of these categories are as follows:

- Grade 1: Mild AE
- Grade 2: Moderate AE
- Grade 3: Severe AE
- Grade 4: Life-threatening or disabling AE
- Grade 5: Death related to AE

Any TEAE will be included in the AE summaries as detailed in Section 4.5.1.

Missing start and stop dates for AEs will be imputed using the rules described in Section 4.1.3.

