#### **3.2.3.1 Possibly-Related Adverse Events**

A PRAE is any TEAE with a relatedness to durvalumab of possible, or where the relatedness is missing. When the relatedness of a TEAE is missing on the electronic Case Report Form (eCRF), all efforts will be taken to ensure that the Investigator assigns his/her assessment of relatedness prior to DBL.

If relatedness of a TEAE is missing at the DBL, as given in Section 4.1.2, the TEAE will be considered as possibly related to durvalumab.

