### 3.5.2 Prior and Concomitant Medications and Therapies

All therapies (drug or non-drug), including herbal preparations, whether prescribed or over-the-counter, that are used during the study will be recorded in the eCRF. Details include generic and/or brand names of medications, WHO drug dictionary encoding, reason for use, route, dose, dosing frequency, and start and stop dates.

Prior therapies are defined as those with at least one dose/treatment taken before the date of the first dose of study medication.

Concomitant therapies are defined as those with at least one dose/treatment taken between the date of first dose (inclusive) and the date of last dose (inclusive) of durvalumab.

[figure not shown]
Missing start and stop dates for medications will be imputed using the rules described in Section 4.1.3.

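### SAP 4.1.3 can move a partly dated AE start to the first-dose date even when the recorded stop is before first dose, giving a start after the stop and a pre-treatment event in the TEAE tables

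*SAP*

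**What the plan says.** SAP 4.1.3 (Handling of Missing Data) opens its start-date rules with "If the start date of the concomitant medication or AE is missing, the following rules will be applied". Three of those rules matter here.

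- **Day missing, month and year known:** impute day 01, "unless month is same as month of first dose of study drug then impute first dose date".
- **Month and day missing, year known:** impute 01 January, "unless year is the same as first dose date then impute first dose date".
- **Start wholly missing, stop known:** "If the start date is completely missing and end date is present, then take day and month as 01Jan and the year from end date". This is the only start-date rule that uses the stop date.

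SAP 3.2.3 (Adverse Events) applies these rules to AE dates. It says that a TEAE "is an AE with an onset date or a pre-existing AE worsening following the first dose of study treatment", through 90 days after the last dose. SAP 4.1.2 uses the imputed dates to derive time to onset and time to resolution. SAP 4.5.1.1 summarises time to first onset and duration for AESI/AEPI.

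On collection, Protocol 8.3.2 states "AEs and SAEs will be collected from the time of the patient signing the ICF until 90 days after the last dose of durvalumab", so AEs that begin and end before dosing are in the database. Protocol 9.5.2.1 says that AEs occurring before treatment are to be listed but kept out of the AE summary tables.

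**The concern.** Imputing the first-dose date is a cautious default when it is unclear whether an event began before or after dosing. A recorded stop before first dose removes that doubt: the onset was also before first dose. The two partial-date rules ignore this. They give a start later than a date already known to be the end, and the onset-based TEAE definition then counts the event as emerging on treatment.

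Such events can occur in this trial. Screening runs from Day -28 to Day -1, and radiotherapy must have finished within 42 days before first dose. Exclusion criterion 10 bars, with exceptions, unresolved Grade 2 or higher toxicity from earlier therapy, so some enrolled patients may have toxicity that cleared shortly before dosing. There is no control arm to offset a pre-treatment event counted against durvalumab.

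At stake are the accuracy of the TEAE tables, false Day 1 onsets, and negative durations in the AESI/AEPI summaries.

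**Working it through.** The plan states no figure on this point, so the check applies the rules literally and then sizes their reach.

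**1. Worked dates.** Take first dose 24 May 2021 and recorded stop 10 May 2021. Duration = stop - start + 1. Onset on the first-dose date is counted as treatment-emergent.

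| Recorded start | Imputed start | TEAE? | Duration (days) |
|---|---|---|---|
| May 2021, day missing | 24 May 2021 | yes | 10 - 24 + 1 = -13 |
| 2021 only | 24 May 2021 | yes | -13 |
| wholly missing | 1 Jan 2021 | no | 130 |

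The record with the least information keeps its dates in order; the two with more information do not. If the start month is earlier than the first-dose month, the missing-day rule gives day 01 of that month and no fault arises.

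The negative duration does not depend on how Day 1 is classed. The TEAE result does: it needs an onset on the first-dose date to count as following first dose, which is the usual reading at date level.

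**2. Share of resolved screening AEs exposed.** Assume that first-dose dates are spread evenly over a 365-day year and that onset is equally likely on each eligible screening day. An AE starting *a* days before first dose (*a* from 1 to 28) starts in the same calendar month with probability 1 - 12*a*/365. An AE whose stop falls *L* days after its start ends before dosing only if *a* runs from *L*+1 to 28, so the mean of *a* is (*L* + 29)/2.

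- *L* = 3: mean 16; 1 - 192/365 = 0.474
- *L* = 7: mean 18; 1 - 216/365 = 0.408
- *L* = 10: mean 19.5; 1 - 234/365 = 0.359

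Weighting every start/stop pair within Days -28 to -1 equally gives a mean *a* of 19 and a share of 1 - 228/365 = 0.375. For the year-only rule the matching share is 1 - 19/365 = 0.948.

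These are shares among resolved screening AEs that already have such a partial start. They do not say how often a partial start occurs.

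**3. Rough count.** The documents give no frequency of screening AEs or of missing start days. As an assumption only, take 20-40 resolved screening AEs among the 102 patients, with 2-10% lacking a start day.

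- Low: 20 x 0.02 x 0.36 = 0.1
- High: 40 x 0.10 x 0.47 = 1.9

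That is roughly 0-2 misdated AEs of any grade.

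**4. Size if one reached the primary count.** One extra patient adds 1/102 = 1.0 percentage point overall, or 1/43 = 2.3 points in the palliative cohort. For illustration, 12/102 is 11.8% (exact 95% CI 6.2-19.6) and 13/102 is 12.7% (7.0-20.8).

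**The case against.** The strongest reply is that the protocol already settles the matter. Protocol 9.5.2.1 excludes pre-treatment AEs from summary tables, Protocol 9.5 requires a TEAE to emerge or worsen after dosing, and SAP section 6 does not withdraw either in its visible text. An event with a recorded stop before first dose is pre-treatment on the recorded data alone, so a careful programmer would not let an imputed date override it. This shows the intent, and it stands as such. It does not repair the SAP rule, which gives no order of precedence, and it leaves the negative duration untouched.

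The second reply is that the effect is small. That is accepted. Start date is a collected variable and missing data are queried, so few partial dates should remain at database lock.

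Three stronger readings are tempting, and the documents do not support them.

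- **Primary endpoint contamination.** A reader might infer it because a PRAE includes a TEAE with possible relatedness "or where the relatedness is missing". But the event must also be Grade 3 or 4. SAP 3.2.3.1 commits the study team to obtaining relatedness before lock, and the causality guide in Protocol Appendix B 7 first asks whether the patient had received the drug. The route is open but remote.
- **Medications losing prior status.** The same rules cover medications, so a reader might infer that one stopped before dosing is no longer prior. SAP 3.5.2 does not classify by start date: "Prior therapies are defined as those with at least one dose/treatment taken before the date of the first dose of study medication". A stop before first dose proves such a dose, so the medication stays prior.
- **Matching on month but not year.** The missing-day rule names only the month, so a start in May 2022 might seem to move to 24 May 2021. That would have the rule overwrite a recorded year. The month of first dose is naturally read as that one calendar month, so only the wording needs tidying.

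**Conclusion.** The point holds for AEs. Followed literally, SAP 4.1.3 gives an AE with a partial start and a recorded pre-dose stop a start later than its stop. With SAP 3.2.3, it can place that AE in the TEAE tables and in the AESI/AEPI onset and duration summaries, contrary to Protocol 9.5.2.1. This is a stated rule that produces a wrong result, not a missing detail.

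The reach is about 36-47% of AEs lasting 3-10 days that resolve in screening, if their start day is missing, under uniform timing. The frequency of missing start days is unknown; the count of about 0-2 events rests wholly on the assumed ranges above. The expected effect on the general safety tables is small, and on the primary endpoint unlikely. The reason to act is that the error is certain whenever the pattern occurs and is easy to prevent.

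**What to change.** In SAP 4.1.3, amend both partial-start rules as follows:

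- Impute the first-dose date only if the stop date is missing or is on or after first dose.
- Otherwise impute the first day of the known month, or 01 January when only the year is known.
- An imputed start may never be later than a known stop date.

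In the example, the missing-day record then starts on 1 May 2021, is not treatment-emergent and lasts 10 - 1 + 1 = 10 days. The year-only record starts on 1 January 2021 and is also not treatment-emergent. An AE with its stop on or after 24 May 2021 is handled as now, so the cautious default is kept wherever onset is truly uncertain.

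As a wording clarification only, have the missing-day rule refer to both month and year.

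The cost is one added clause and one programming condition, with no new data.

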### **4.3 Analysis of Primary Safety Endpoint**

The primary endpoint of this study is the incidence of Grade 3 and Grade 4 PRAEs (see Section 3.2.3.1) which occur within the first six months (ie, up to and including the 183rd day) after the initiation of durvalumab. Any Grade 3 or Grade 4 PRAEs which started after the 183rd day of the study, or after the 90th day following discontinuation of durvalumab, or after the start of subsequent anti-cancer therapy will not be included.

The number and percentage (and exact Clopper-Pearson 95% CI) of patients with NCI CTCAE Grade 3 or Grade 4 PRAEs, both overall and for those occurring within the first six months after initiation, will be summarized for the SAF for all patients and within the standard and palliative radiotherapy cohorts. This summary will also be graphically presented as a bar chart. The

number and percentages of patients with NCI CTCAE Grade 3 or Grade 4 PRAEs will also be summarized by SOC and PT.

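### When an AE has no start date, SAP 4.1.3 imputes 1 January of its end year with no first-dose exception, so an event that ended on treatment in the first-dose year can drop out of the primary count

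*SAP*

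**What the plan says.** SAP 4.1.3 lists four rules for a missing start date of an AE or concomitant medication:

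1. Year missing: "If the year is missing, the year should be imputed as the year that patient received the first dose of durvalumab".
2. Only the year known: "impute the month as January and the day as 01 unless year is the same as first dose date then impute first dose date".
3. Year and month known: first of the month, "unless month is same as month of first dose of study drug then impute first dose date".
4. Nothing known about the start, but an end date recorded: "start date is completely missing and end date is present, then take day and month as 01Jan and the year from end date".

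Rules 2 and 3 carry a first-dose exception; rule 4 does not. No order of precedence is given, although a wholly missing start also has a missing year and so meets rule 1.

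SAP 3.2.3 applies these rules to AEs: "Missing start and stop dates for AEs will be imputed using the rules described in Section 4.1.3". The same section defines a treatment-emergent AE (TEAE) as "an AE with an onset date or a pre-existing AE worsening following the first dose of study treatment", up to 90 days after the last dose. SAP 3.2.3.1 adds: "A PRAE is any TEAE with a relatedness to durvalumab of possible, or where the relatedness is missing". SAP 4.3 counts Grade 3 or 4 possibly related AEs (PRAEs) up to and including Day 183, and selects on onset: "Any Grade 3 or Grade 4 PRAEs which started after the" 183rd day are excluded.

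**The concern.** The start date about which least is known gets the least protection. An event known to have ended on treatment, and judged possibly caused by durvalumab, can be dated months before the first infusion. The chain from onset to TEAE, from TEAE to PRAE, and from PRAE to the primary count then removes it.

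For an event that ended on treatment in the first-dose year, the error can only remove it. That is the opposite of how the SAP treats missing causality, which counts as related (SAP 3.2.3.1 and 4.1.2). The event would still be listed and flagged as pre-treatment (SAP 4.5.1), but Protocol 9.5.2.1 keeps pre-treatment AEs out of the summary tables and no step returns the event to the primary count. At stake is the single primary safety figure, overall and in each cohort.

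**Working it through.** **Baseline check.** SAP 1.3 gives an exact 95% CI of 5% to 23% for 12% of 60 patients. Clopper-Pearson with x = 0.12 × 60 = 7.2 gives 5.0 to 23.0, so the method used below agrees with the plan.

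**The rule on one example.** First dose 15 Jun 2021; AE ended 10 Sep 2021, which is Day 88; start wholly missing.
- Rule 4 imputes 01 Jan 2021, 31 + 28 + 31 + 30 + 31 + 14 = 165 days before first dose: not a TEAE, so not counted.
- With the exception of rules 2 and 3, onset would be 15 Jun 2021 (Day 1): a TEAE inside the window.

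**How general this is.** Take every first-dose day in a 365-day year and every end date on Days 1-183. Of 50,142 pairs with both dates in the same year, rule 4 puts 49,959 (99.6%) before first dose. The other 183 are first doses on 1 January.

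**Size per patient lost.** Sample sizes are from SAP 1.3 (102 treated; 59 and 43 by cohort). Counts are illustrative, near 12%.

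| Group | Before (95% CI) | One patient lost (95% CI) | Shift |
|---|---|---|---|
| All | 12/102 = 11.8% (6.2-19.6) | 11/102 = 10.8% (5.5-18.5) | 1.0 point |
| Standard | 7/59 = 11.9% (4.9-22.9) | 6/59 = 10.2% (3.8-20.8) | 1.7 points |
| Palliative | 5/43 = 11.6% (3.9-25.1) | 4/43 = 9.3% (2.6-22.1) | 2.3 points |

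**Does adding the exception help on balance?** This needs assumptions that the documents do not give: first doses spread evenly over a year, true onset uniform within the stated range, and AE durations of 14, 30, 60 or 120 days. Simulating 2,000,000 triggering AEs per setting gives, per triggering AE (not per patient):

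| | 14 d | 30 d | 60 d | 120 d |
|---|---|---|---|---|
| True onset Days 1-183: dated before first dose now | 71% | 67% | 59% | 42% |
| Same, with the exception | 0% | 0% | 0% | 0% |
| True onset Days 184-337: counted in Days 1-183 now | 50% | 50% | 49% | 43% |
| Same, with the exception | 75% | 71% | 63% | 46% |

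Let g be the share of early-onset events rescued and h the extra share of late-onset events wrongly counted. The exception gives fewer errors when the early-onset share exceeds h / (g + h). For 14 days that is 0.251 / (0.713 + 0.251) = 0.26. For the four durations the thresholds are 26%, 24%, 19% and 8%. Protocol 4.2.1 says that most immune-mediated AEs in PACIFIC fell in the first 6 months. That suggests a share above these thresholds, though such events are not all Grade 3/4 PRAEs.

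**Secondary point: stop dates.** Duration is taken as stop − start + 1 (assumed; the SAP gives no formula), with last dose on 5 Mar 2022.
- Onset 20 Mar, stop recorded only as March 2022: imputed stop 5 Mar, duration 5 − 20 + 1 = −14 days.
- Onset 20 Apr, resolved, stop wholly missing: imputed stop 6 Mar, duration −45 + 1 = −44 days.

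These would enter the AESI/AEPI durations of SAP 4.5.1.1. They do not touch the primary endpoint.

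**The case against.** - **Rule 1 may already cover the case.** Rules 1 and 2 together would give the first dose date. But rule 4 describes this case exactly and is the natural one to follow. With no stated precedence, two programmers could reach different primary counts, so the overlap is itself a reason to amend.
- **Imputed dates may not be meant to decide TEAE status.** SAP 4.1.2 mentions imputing partial dates for time to onset and time to resolution, and Protocol 9.5 defines TEAEs by presence at baseline. Yet SAP 3.2.3 invokes the 4.1.3 rules for AE dates in the section that defines a TEAE, and the SAP names no other way to classify an event with no start date.
- **A worsening dated after first dose keeps the event in.** This stands: Protocol 8.3.4 collects changes in grade. It does not help an event recorded at a single grade.
- **The current rule also errs the other way, and the exception adds to that.** This stands. Of events with true onset in Days 184-337, 43 to 50% are already counted wrongly, and the exception raises this to 46 to 75%.
- **Events that cross the year end stay unfixed.** This stands. With first dose on or before 2 July, 1 January of the next year is after Day 183, so an early event that ended the next year is still lost. In the simulation this affects 0.1 to 10.7% of early-onset events under either rule.
- **It may never happen.** Start dates are collected (Protocol 8.3.4) and missing data are queried (Protocol 9.7). This limits the weight of the point. It does not make the rule right when it is used.

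**Conclusion.** The point holds and is minor. As written, rule 4 removes from the primary count a Grade 3 or 4 possibly related AE with no start date that ended on or after first dose in the first-dose year, unless first dose was on 1 January or a later worsening is recorded. If the AE ended before first dose, pre-treatment status is correct and nothing is lost.

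The wording gap is certain. Its effect on the result is not: the documents do not say how many AEs will lack a start date. The net benefit of the exception rests on the assumed spread of first doses, onset times and AE durations.

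**What to change.** In SAP 4.1.3:
- Add to rule 4, for AEs: *unless the end date is on or after first dose and in the same calendar year, in which case impute the first dose date*.
- State that rule 4 takes precedence over rules 1 and 2 when an end date is present.
- Require any imputed stop date to be no earlier than the start date.

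In SAP 4.3, report the number of Grade 3/4 PRAEs with an imputed onset, and the primary count with and without them. This shows any over-counting that the exception introduces: events that truly began before first dose, or after Day 183 in the first-dose year, would count from Day 1.

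The cost is a few sentences in the SAP and a little programming. The protocol, the endpoint and data collection are unchanged.

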9.4 Outcome measures for analyses

- 1 **AE:** Number and proportion of patients with AEs in total and by causality and severity
- 2 **AE:** Number and proportion of patients with Grade 3 and Grade 4 AEs in total and by causality
- 3 **SAE:** Number and proportion of patients with SAEs in total and by causality and severity
- 4 **AEs leading to death:** Number and proportion of patients with AEs leading to death
- 5 **AEs leading to treatment interruption or discontinuation:** Number and proportion of patients with AEs leading to treatment interruption and/or discontinuation
- 6 **AESI:** Defined as an AE of scientific and medical interest specific to understanding of the IP. AESIs for durvalumab include, but are not limited to, events with a potential inflammatory or immune-mediated mechanism and which may require more frequent monitoring and/or interventions such as steroids, immunosuppressants, and/or hormone replacement therapy. In order to further characterize safety objectives related to AESIs, outcome measures will be assessed, which may include (and are not necessarily limited to) the following:
 - (a) Number and proportion of patients with AESIs, by predefined type (or newly defined by this study) in total and by seriousness, severity and causality, including immune-relatedness;

- (b) Number and proportion of patients who received steroids, immunosuppressants, and/or hormone replacement therapy to manage AESIs;
- (c) Time from start of durvalumab to the onset of an AESI predefined type, all interventions of AESIs by type of intervention (including intervention with steroids, immunosuppressants, and/or hormone replacement therapy), and time from onset of an AESI type to resolution;
- (d) Duration of the intervention with steroids, immunosuppressants, and/or hormone replacement therapy until the resolution of AESI;
- (e) The imAEs will be assessed as a subset of AESIs. An imAE is defined as an AESI that is associated with drug exposure and is consistent with an immune-mediated MOA and where there is no clear alternate etiology.
- (f) Laboratory findings, vital signs, and other safety parameters associated with AESIs will be summarized as part of the AESI outcome measures.

7 **PFS:** Defined as the time from the first date of treatment until the date of objective disease progression or death (by any cause in the absence of progression) regardless of whether the patient withdraws from IP or receives another anticancer therapy prior to progression.

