#### 4.5.1.1 Adverse Events of Special Interest and Possible Interest

Preferred terms used to identify adverse events of special interest and possible interest (as defined in 3.2.3) will be listed before DBL and documented in the Study Master File. Grouped summary tables of certain MedDRA preferred terms will be produced and may also show the individual preferred terms which constitute each AESI/AEPI grouping. Groupings will be based on preferred terms provided by the medical team prior to DBL, and a listing of the preferred terms in each grouping will be provided.

Summaries of the above-mentioned grouped AE categories will include number (%) of patients who have:

- Any AESI/AEPI
- Any AESI/AEPI by SOC, PT and maximum CTCAE grade
- Any AESI/AEPI of maximum CTCAE grade 3 or 4
- Any serious AESI/AEPI
- Any AESI/AEPI with outcome of death
- Any AESI/AEPI possibly related to study treatment
- Any AESI/AEPI leading to concomitant medication use (steroids)
- Any AESI/AEPI leading to concomitant medication use (high dose steroids)
- Any AESI/AEPI leading to concomitant medication use (endocrine therapy)
- Any AESI/AEPI leading to concomitant medication use (other immunosuppressants)
- At least one AESI/AEPI leading to discontinuation of study treatment
- Possibly related AESI/AEPI leading to discontinuation of study treatment
- Time to onset of first AESI/AEPI (days)
- Duration (days) of AESI/AEPI

An overall AESI/AEPI summary will be presented, including number and percentage of patients in each of these categories. Any AESI/AEPI presented by outcome will also be provided.

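### The stop-date rules in SAP 4.1.3 anchor incomplete AE end dates to the last durvalumab dose, so some AESI/AEPI and imAE durations come out negative, truncated or overstated

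*SAP*

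**What the plan says.** SAP 3.2.3 applies the rules to adverse events: "Missing start and stop dates for AEs will be imputed using the rules described in Section 4.1.3". For stop dates, SAP 4.1.3 has three rules tied to the last dose:

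- **Day missing:** last day of the recorded month, "unless month is same as month of last dose date then impute last dose date".
- **Month and day missing:** 31 December of the recorded year, "unless year is the same as last dose date then impute last dose date".
- **Wholly missing, event has stopped:** "if it started on or after first dose date then impute a date that is 1 day after the last dose date".

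There is one exception to the third rule: "If the ongoing flag is missing then assume that AE is still present / medication is still being taken". In that case no date is imputed.

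SAP 3.2.3 counts as treatment-emergent an AE that begins or worsens "following the first dose of study treatment through to 90 days after the last dose of durvalumab". SAP 4.1.2 says that imputed dates are used to derive time to resolution and time to onset. SAP 4.5.1.1 plans a summary of "Duration (days) of AESI/AEPI", and SAP 4.5.1.2 plans similar summaries for imAEs. Protocol 9.4, item 6(c), names time from AESI onset to resolution as an outcome measure.

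**The concern.** The rules treat the last dose as a natural end for an event whose stop date is incomplete. The rest of the plan does not: it follows AEs for 90 days after the last dose and counts onsets in that period. Neither document requires an imputed stop date to be on or after the start date. Applied literally, the rules can therefore give an event an end before its beginning.

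The planned AESI/AEPI and imAE durations and time to resolution are at stake. Negative values cannot be reported, so programmers would need a repair that the SAP does not specify, chosen after the data are seen. Truncated values are harder to catch, because they look plausible in a table.

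**Working it through.** The documents give no figure for this rule, so there is nothing of the plan's own to reproduce. The three rules were applied literally to worked dates. The SAP gives no formula for AESI duration. Duration is taken as stop - start + 1, the convention the SAP uses for its other intervals.

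**Worked cases, last dose 4 Feb 2022 (first dose 5 Mar 2021)**

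| Case | Onset | True stop | True days | Day missing | Month and day missing | Wholly missing, stopped |
|---|---|---|---|---|---|---|
| A: starts after last dose, same month | 10 Feb 2022 | 25 Feb 2022 | 16 | -5 | -5 | -4 |
| B: starts after last dose, later month | 10 Mar 2022 | 20 Apr 2022 | 42 | 52 | -33 | -32 |
| C: starts on treatment, outlasts last dose | 20 Jan 2022 | 20 Apr 2022 | 91 | 101 | 16 | 17 |
| D: resolved long before last dose | 1 Jun 2021 | 20 Jun 2021 | 20 | 30 | 214 | 250 |

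In case A with the day missing, the imputed stop is 4 Feb and 4 - 10 + 1 = -5. With the stop wholly missing it is 5 Feb and 5 - 10 + 1 = -4. In case C with month and day missing, 20 Jan to 4 Feb is 15 + 1 = 16 days, against a true 91.

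**General result for onset k days after the last dose (k = 1 to 90)**

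- Where the month or year matches that of the last dose, the imputed stop is the last dose date. The stop precedes the start by k days: up to 90 under the year-only rule, and at most 31 - 1 = 30 under the day-missing rule, because start and stop must then lie in one calendar month.
- Where the stop is wholly missing and the event has stopped, the imputed stop is last dose + 1. The stop precedes the start by k - 1 days, up to 89. At k = 1 the two coincide and the duration is 1 day. This is the only case in which a last-dose rule does not reverse the dates of an event starting after the last dose.

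**How often each rule reverses the dates (simulation; all ranges are assumptions)**

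The last dose is uniform over a calendar year, and every event starts after the last dose and has an incomplete stop date of the stated type.

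| Assumed onset after last dose; days from start to stop | Day missing | Month and day missing | Wholly missing, stopped |
|---|---|---|---|
| 1-90 days; 0-59 days | 2.9% | 79.6% | 98.9% |
| 1-30 days; 0-29 days | 17.1% | 91.8% | 96.6% |

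The last column agrees with direct calculation: only k = 1 escapes, so 89/90 = 98.9% and 29/30 = 96.7%. The year-only and wholly missing rules cause most of the reversals. A missing day in a later month goes to month end and comes out somewhat long, as in case B.

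**The case against.** The best defence is that few records should reach these rules. Protocol 8.3.4 collects start and stop dates for every AE, Protocol 8.3.3 follows AESIs to resolution or stabilization, and Protocol 9.7 provides for queries on missing or impossible data. A wholly missing stop date with no ongoing flag is not imputed. SAP 4.5.1 drops events after subsequent therapy from most AE summaries, and SAP 4.1.2 keeps partial dates as reported in the listings. All of this stands and limits the number of cases. It does not correct what the rules do to the records that remain.

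A reader might also infer three stronger things that the documents do not support.

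- **That durations are biased short overall.** Case D shows the opposite error: 20 days becomes 250. The net direction depends on when events occur relative to the last dose, and the documents do not give this.
- **That the duration of rescue steroids is distorted.** Protocol 9.4, item 6(d), lists "Duration of the intervention with steroids, immunosuppressants, and/or hormone replacement therapy until the resolution of AESI", but among measures that may be included. SAP 3.5.2 does send missing medication dates to the same rules. However, it defines concomitant therapy as needing at least one dose between the first and last durvalumab dose, which leaves out a steroid begun afterwards. SAP 4.5.1.1 summarises steroid, endocrine and immunosuppressant use as numbers of patients. No planned SAP summary of steroid duration is shown to be affected.
- **That the primary endpoint is touched.** SAP 3.2.1 and 4.3 decide inclusion from when the PRAE started, not from when it stopped.

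**Conclusion.** The rules are wrong as written. For an AE that starts after the last dose, each last-dose rule, when it applies, places the stop before the start by up to 90 days. The sole exception is onset one day after the last dose with a wholly missing stop date. AEs that began on treatment and outlasted the last dose are truncated (91 days becomes 16 or 17 in case C), and AEs that resolved long before it can be overstated.

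The reach is limited to descriptive output: AESI/AEPI and imAE durations and time to resolution. The primary endpoint and AE incidence do not change. The number of incomplete stop dates is not given, so the effect on any summary cannot be stated. The simulated percentages rest on assumed onset and length ranges and are conditional on a stop date being incomplete. The finding that dates reverse does not rest on those assumptions; it follows from the text of the rules.

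**What to change.** Reword the stop-date bullets in SAP 4.1.3 as follows.

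- **Partial stop date:** impute the latest date compatible with the recorded month or year, limited by death, DCO or last contact where that does not contradict the recorded part.
- **Every imputed stop date:** never earlier than the recorded or imputed start date.
- **Wholly missing stop date of an event marked as stopped:** do not impute; treat the duration as missing or censored.

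In case A with the day missing, this gives 28 Feb 2022 and 28 - 10 + 1 = 19 days, against a true 16 and the current -5.

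The change needs a few reworded bullets and no new data. Its cost is that some imputed durations become longer and some are reported as missing or censored. The lengthening can be large for year-only dates: case A with only 2022 recorded would run to 31 December, day 365 - day 41 + 1 = 325 days, unless death, DCO or last contact comes first. Showing the number of imputed and censored stop dates beside each duration summary would make that dependence visible.
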